	
• Grade 3 or higher non-hematologic toxicity that are considered at least possibly related to Ibrutinib with the exception of nausea, vomiting, diarrhea, or electrolyte abnormality, unless these persist for at least 3 days despite maximal supportive care• Any grade 3 or higher fungal or bacterial infection (excluding line infection, catheter-associated UTI, or C difficile infection), cardiac toxicity (with the exception of hypertension) or bleeding regardless of the attribution. We note, though, that many patients in the hospital that develop infection of any grade will be treated with IV antibiotics, and that per CTCAE criteria, those graded 3 or higher would be those where IV antibiotics are indicated, not only for those where IV are chosen due to convenience.• Grade 3 or higher hemorrhage regardless of attribution, or Grade 2 hemorrhage that is considered at least possibly related to ibrutinib and is considered to be significant by the treating physician in collaboration with the PI.• Non COVID-19 related neutropenic fever 
Enrollment to this dose level will stop if 2 of the first 3 evaluable patients or if at least 33% of subsequent evaluable patients (i.e, 2/6, 3/9, or 4/12) have DLT. If unacceptable toxicity is observed, Ibrutinib will decrease to 280 mg daily, and another 12 patient lead-in will be evaluated at this lower dose level following the same stopping rules. If toxicity is acceptable, the study will proceed to the randomized component. Patients who do not receive 14 days of Ibrutinib for reasons other than toxicity or DLT will be replaced for the purposes of the safety and tolerability assessment.
 
Randomized Double-Blind Phase 2 Study
 
The main study is a randomized, double-blind placebo-controlled trial. Following completion of the safety lead-in, patients in the phase 2 portion will be randomized in a 1:1 fashion to receive ibrutinib plus standard treatment (Arm A) versus placebo plus standard treatment (Arm B) for COVID-19.
 
Patients may receive any additional therapies that are not prohibited in the section on concomitant medications.
 
In this trial, cycles will be 7 days in length. Study drug will continue for 2 cycles (14 days).

--	--

Accrual Expectations, N	78

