Concern for administering ibrutinib or even more selective BTK inhibitors for the treatment of COVID-19 syndrome includes 1) impairment of humoral or cellular immune

response to SARS-COV-2 virus; 2) overlapping cardiac toxicity that might occur with viral induced cardiac symptoms and also therapeutics such as chloroquine and hydroxychloroquine; 3) increased bleeding given the presence of thrombocytopenia with severe cases; 4) increase in alternative infections arising from the anti-inflammatory response to ibrutinib and other BTKi. A small study examining the response of CLL patients on ibrutinib vaccinated against influenza A demonstrated protective titers in up to 74% of patients⁴⁶. In a prospective study performed by our own group in early stage CLL not requiring therapy, ibrutinib was administered concurrently with prenar-13 vaccine and compared to sequential prevnar 13 followed by ibrutinib. In the concurrent arm, 15/16 patients showed a significant increase in antibody titer following vaccination whereas in the sequential arm 3/13 patients had an increase in antibody titer. Additionally, long-term treatment with both ibrutinib and acalabrutinib does not significantly impair humoral function and results in elevated serum IgA levels among non-heavily pretreated patients^{47,48}. This trial will include monitoring of IgM and IgG response to SARS-CoV2 among recovering patients as one of the secondary endpoints to assure diminished response is not noted. With short exposure to ibrutinib (14 days for most), we do not anticipate this will occur and believe the risk population justifies this inclusion. While cardiac toxicity consisting predominately of hypertension or atrial fibrillation and much lesser frequency of ventricular tachycardia and rare cardiomyopathy⁴⁹⁻⁵². The risk of atrial fibrillation is approximately 3-10% and occurs over an extended period of time. Prolongation of QT is uncommon with ibrutinib. To minimize risk we will exclude patients with recent myocardial infarct, symptomatic congestive heart failure, and also poorly controlled or patients at high risk for ventricular arrhythmias. Patients with COVID-19 are in the hospital and can be closely monitored for both arrhythmia and functional cardiac problems. Given the short period of ibrutinib treatment (14 days for most), the cardiac risks seem justifiable given the high mortality associated with hospitalized COVID-19 patients with cancer. While serious bleeding has uncommonly been observed with ibrutinib therapy⁵³⁻⁵⁵, efforts to risk mitigate this by pausing therapy for surgical procedures and also avoiding anticoagulation with warfarin and other agents has greatly diminished this risk. The pathology of lung and organ failure in COVID-19 syndrome can involve microthrombi that ibrutinib may have some protective effect against. Indeed, a collective experience by our group at OSU with ibrutinib demonstrated that CLL patients had a very low level of venous or arterial thrombosis as compared to historical controls⁵⁶. To mitigate risk of serious CNS bleeding we will exclude patients with recent stroke (hemorrhagic), congenital or acquired bleeding diathesis. Patients will be monitored for bleeding and if excessive events are noted the study will be put on hold and re-evaluated. Finally, the concern for secondary infection with ibrutinib must be considered in the context of significant clinical experience with this agent in different lymphoid malignancies where over time the frequency of infections significantly diminishes. However, heavily pre-treated patients and those who have received steroids concurrently are probably more at risk^{57,58}. Given the short duration of ibrutinib in this trial (14 days for most patients), we do not anticipate that the risk of such infections will be high. We will monitor for these and adjust the trial if observed.

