7. TREATMENT PLAN

7.1. Overview and Design of Study

7.1.1 Phase 1b

This study will begin with a 12 patient lead-in cohort to establish safety and better characterize toxicity prior to the randomized component. For safety purposes, patients will be enrolled in cohorts of 3 for the first 6 patients, and patients will receive ibrutinib at a dose of 420 mg daily. Dose limiting toxicity (DLT) will be evaluated during the first 14 days of treatment.

DLT would be considered to be any of the following:

- Grade 4 hematologic toxicity that persists for 3 or more days that is considered at least possibly related to ibrutinib.
- Grade 3 or higher non-hematologic toxicity that are considered at least possibly related to Ibrutinib with the exception of nausea, vomiting, diarrhea, or electrolyte abnormality, unless these persist for at least 3 days despite maximal supportive care
- Any grade 3 or higher fungal or bacterial infection (excluding line infection, catheter-associated UTI, or C difficile infection), cardiac toxicity (with the exception of hypertension) or bleeding regardless of the attribution. We note, though, that many

patients in the hospital that develop infection of any grade will be treated with IV antibiotics, and that per CTCAE criteria, those graded 3 or higher would be those where IV antibiotics are indicated, not only for those where IV are chosen due to convenience.

- Non COVID-19 related neutropenic fever

Further enrollment to this dose level will stop if 2 of the first 3 evaluable patients or if at least 33% of subsequent evaluable patients (i.e, 2/6, 3/9, or 4/12) have DLT. If unacceptable toxicity is observed, Ibrutinib will decrease to 280 mg daily, and another 12 patient lead-in will be evaluated at this lower dose level following the same stopping rules. If toxicity is acceptable, the study will proceed to the randomized component. Patients who do not receive 14 days of Ibrutinib for reasons other than toxicity or DLT will be replaced for the purposes of the safety and tolerability assessment.

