7.3. Concomitant Medication Use Guidelines For Study Participants

Warfarin is excluded throughout the trial as is grapefruits and grapefruit juice, starfruit, and Seville oranges. Cancer therapy is also prohibited during the study. Medications allowed with caution are found in Appendices

A. All concomitant medications need to be documented in the electronic medical record.

Standard of Care COVID 19 Therapy

All standard of care therapy for COVID 19 that is not specifically prohibited in the protocol is acceptable and encouraged. Current standards of care can be found in Table 2 of Appendix C. It is acknowledged that standards of care are likely to change during the course of the study. Standard of care therapy should be considered in the context of toxicities expected with ibrutinib, and therapies that are expected to have overlapping toxicities should be used with caution.

Anticoagulants and Anti-platelet agents

Laboratory studies have shown that *in vitro* ibrutinib can prevent platelets from aggregating normally. While serious bleeding has been uncommon in patients treated to date, it is possible that treatment with the study drug could increase the risk of bruising or bleeding, particularly in subjects receiving oral anticoagulants or antiplatelet agents. Besides warfarin, which is prohibited, patients on the study may receive any other anticoagulants or antiplatelet agents at prophylactic or therapeutic doses. Subjects receiving anticoagulants and/or antiplatelet agents in conjunction with ibrutinib should be observed closely for any signs of bleeding or bruising and ibrutinib should be withheld in the event of any significant

bleeding events. Patients receiving both therapeutic anticoagulation and anti-platelet agents should be considered at higher risk for bleeding.

Inhibitors or inducers of CYP3A

As ibrutinib is primarily metabolized by CYP3A. Concomitant use of ibrutinib and drugs that strongly or moderately inhibit CYP3A can increase ibrutinib exposure, these should be avoided as possible. Avoid grapefruit and Seville oranges during ibrutinib treatment as these contain moderate inhibitors of CYP3A. Strong inhibitors of ibrutinib should be avoided during the course of the trial. Dose adjustment of ibrutinib due to concomitant use of CYP3A inhibitors should follow Table 1 below as applicable. See Appendices

A for a summary of cautionary medications.

Table 1: Ibrutinib Dose Modification Guidance for Co-Administration with CYP3A Inhibitors

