13. STATISTICAL CONSIDERATIONS

This study will enroll high-risk cancer patients testing positive for COVID-19, to be treated with ibrutinib plus standard of care therapy for COVID-19 or placebo plus standard of care therapy for COVID-19. There will be two components of the trial: 1) a safety lead-in component to evaluate the feasibility and tolerability of administering ibrutinib with standard therapy for COVID-19 and 2) a double-blinded randomized component to assess efficacy of ibrutinib with standard therapy for COVID-19 versus placebo plus standard therapy for COVID-19.

Safety Lead-in Cohort

This study will begin with a 12 patient lead-in cohort to establish safety and better characterize toxicity. Patients will receive Ibrutinib at a dose of 420mg daily. For safety purposes, patients will be enrolled in cohorts of 3 for the first 6 patients, with a pause in study enrollment after each cohort to assess for dose-limiting toxicity (DLT). DLT will be evaluated during the first 14 days of treatment.

DLT would be considered to be any of the following:

- Grade 4 hematologic toxicity that persists for 3 or more days that is considered at least possibly related to ibrutinib.
- Grade 3 or higher non-hematologic toxicity that are considered at least possibly related to Ibrutinib with the exception of nausea, vomiting, diarrhea, or electrolyte abnormality, unless these persist for at least 3 days despite maximal supportive care
- Any grade 3 or higher fungal or bacterial infection (excluding line infection, catheter-associated UTI, or C difficile infection) or cardiac toxicity (with the exception of hypertension) regardless of the attribution. We note, though, that many patients in the hospital that develop infection of any grade will be treated with IV antibiotics, and that per CTCAE criteria, those graded 3 or higher would be those where IV antibiotics are indicated, not only for those where IV are chosen due to convenience.
- Grade 3 or higher hemorrhage regardless of attribution, or Grade 2 hemorrhage that is considered at least possibly related to ibrutinib and is considered to be significant by the treating physician in collaboration with the PI.
- Non COVID-19 related neutropenic fever

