Enrollment to this dose level will stop if 2 of the first 3 evaluable patients or if at least 33% of subsequent evaluable patients (i.e, 2/6, 3/9, or 4/12) have DLT. If unacceptable toxicity is observed, Ibrutinib will decrease to 280 mg daily, and another 12 patient lead-

in will be evaluated at this lower dose level following the same stopping rules. If acceptable toxicity is observed, the study will proceed to the randomized component. Patients who do not receive 14 days of Ibrutinib for reasons other than toxicity or DLT will be replaced for the purposes of the safety and tolerability assessment.

Randomized Phase 2

The main study is a randomized, double-blind placebo-controlled trial. The primary endpoint of the phase 2 component is the proportion of randomized patients with respiratory failure or death during hospitalization for COVID-19 infection within 30 days of registration. Respiratory failure is defined as any of the following: 1) endotracheal intubation and mechanical ventilation, 2) extracorporeal membrane oxygenation, 3) high-flow nasal cannula oxygen delivery (i.e., reinforced nasal cannula delivering heated, humidified oxygen with fraction of delivered oxygen ≥ 0.5 and flow rates of ≥ 30 l/min), noninvasive positive pressure ventilation, or 4) clinical diagnosis of respiratory failure without initiation of one of above measures only when clinical decision-making is driven solely by resource limitation or if patient has DNI (Do Not Resuscitate) status. Patients will be randomized to each treatment arm in a 1:1 ratio utilizing a permuted block schedule. Randomization will be stratified on age (<60 years vs ≥ 60 years) and presence of comorbidities (yes vs no) (comorbidities defined in Appendix C).

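### The DLT list in Section 7.1.1 leaves out the significant grade 2 hemorrhage that the synopsis and Section 13 count, and nothing says which list decides the 420 mg dose

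*Combined protocol and SAP*

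**What the plan says.** DLTs in the lead-in are defined in three places: the synopsis (Trial Design), Section 7.1.1 and Section 13 (Safety Lead-in Cohort).

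- **Section 13** has a separate hemorrhage bullet: "Grade 3 or higher hemorrhage regardless of attribution, or Grade 2 hemorrhage that is considered at least possibly related to ibrutinib", provided the grade 2 bleed is also judged significant by the treating physician with the PI. Its infection and cardiac bullet does not mention bleeding; it ends "or cardiac toxicity (with the exception of hypertension) regardless of the attribution".
- **The synopsis** has the same hemorrhage bullet ("or Grade 2 hemorrhage that is considered at least possibly related to ibrutinib"). Its infection and cardiac bullet also names bleeding at grade 3 or higher.
- **Section 7.1.1** has four bullets and no hemorrhage bullet. Bleeding appears only inside the grade 3 or higher infection bullet: "cardiac toxicity (with the exception of hypertension) or bleeding regardless of the attribution".

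The same rule follows each list. Section 7.1.1 states "Further enrollment to this dose level will stop if 2 of the first 3 evaluable patients" and Section 13 states "Enrollment to this dose level will stop if 2 of the first 3 evaluable patients". Both then give limits of 2/6, 3/9 and 4/12. Meeting a limit lowers the dose to 280 mg and starts another 12-patient lead-in.

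**The concern.** A patient with a possibly related, significant grade 2 bleed has a DLT under two lists and none under the third. The third list is in the treatment plan, where staff running the lead-in would naturally look, and it is the more permissive one. The DLT count decides whether 420 mg stays open, and the dose chosen carries into the randomized part, so one patient's data could support two different dose decisions.

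The classification also affects that patient's own care. The heading of Section 8 limits dose modification in the lead-in to patients without a DLT. Under Section 7.1.1 this patient therefore falls under Section 8, where the interruption rule for non-hematologic toxicity (8.1) starts at grade 3. Under Section 13 the patient has a DLT and Section 8 does not apply.

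Bleeding is one of the four risks that Section 4.5 names for this drug in this disease. The trial admits patients with platelets down to 50,000/mm³ and allows therapeutic anticoagulants other than warfarin.

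**Working it through.** **Step 1: can any bullet of Section 7.1.1 catch the bleed?**

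| Section 7.1.1 bullet | Covers a grade 2 hemorrhage? |
|---|---|
| Grade 4 hematologic toxicity lasting 3 or more days | No |
| Related non-hematologic toxicity, grade 3 or higher | No |
| Infection, cardiac toxicity or bleeding, grade 3 or higher | No |
| Neutropenic fever not due to COVID-19 | No |

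Grade 3 or higher bleeding of any attribution is a DLT in all three lists, so the difference is exactly the significant, possibly related grade 2 bleed. Every Section 7.1.1 DLT is also a Section 13 DLT, so disagreement runs one way: Section 13 stops and Section 7.1.1 continues.

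**Step 2: when does one such bleed change the decision?** It does so when the other DLTs are one below a limit: 1/3, 1/6, 2/9 or 3/12.

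**Step 3: how often is that?** The plan gives no operating characteristics for the lead-in, so there is no stated figure to reproduce. Inputs:

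- looks at 3, 6, 9 and 12 patients with limits 2, 2, 3 and 4 (from the plan);
- one patient with only the grade 2 bleed, equally likely to be in any of the four groups of three (assumed);
- each of the other 11 has a Section 7.1.1 DLT independently with probability p (assumed).

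Disagreement means that Section 7.1.1 passes all four looks while Section 13 stops at one of them.

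Worked case, p = 0.10, bleed among patients 1–6. Five others are seen by the second look.

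- One other DLT among the five: 5(0.1)(0.9)⁴ = 0.32805. Section 13 stops by the second look. Section 7.1.1 passes the remaining looks with probability 0.729 × 0.999 + 0.243 × 0.972 = 0.96447. Product: 0.3164.
- None among the five: 0.9⁵ = 0.59049. Section 13 then stops later, and Section 7.1.1 does not, with probability 0.027 × 0.972 + 0.243 × 0.027 + 0.729 × 0.001 = 0.03353. Product: 0.0198.
- Sum: 0.3362. It is the same for a bleed in the first or the second group of three.

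A bleed among patients 10–12 requires three other DLTs at the last look without an earlier stop: 0.10044 × 0.18 + 0.38742 × 0.01 = 0.0220. A bleed among patients 7–9 gives 0.0779 by the same enumeration. The average is (0.3362 + 0.3362 + 0.0779 + 0.0220)/4 = 0.193.

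| Assumed rate of other DLTs | Opposite decisions, given one such bleed |
|---|---|
| 0% | 0 |
| 5% | 0.112 |
| 10% | 0.193 |
| 20% | 0.251 |
| 25% | 0.235 |
| 30% | 0.199 |

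**Step 4: without conditioning on a bleed.** Let such bleeds add 1 or 2 percentage points to the per-patient DLT rate (also assumed). The probability of stopping 420 mg becomes:

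| DLT rate under 7.1.1 | Stop under 7.1.1 | With 1 point added | With 2 points added |
|---|---|---|---|
| 5% | 0.035 | 0.049 | 0.066 |
| 10% | 0.128 | 0.152 | 0.177 |
| 20% | 0.408 | 0.438 | 0.468 |

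The differences run from about 1.5 to 6 percentage points. They grow with the assumed bleeding rate: 5 points added to a 10% base moves the stop probability from 0.128 to 0.259.

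**The case against.** The gap is narrow. It covers only grade 2 bleeds that are possibly related and judged significant. Two of the three lists agree, one of them in the statistical section, and the adverse event rule for the randomized part in Section 13 also counts significant grade 2 hemorrhage. The wider definition is therefore probably intended. The 11% to 25% takes the bleed as given; without that condition the effect is a few percentage points unless such bleeds are common.

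Other safeguards exist:

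- Section 7.3, for patients on anticoagulants or antiplatelet agents, says "ibrutinib should be withheld in the event of any significant" bleeding event.
- Section 4.5 says that "if excessive events are noted the study will be put on hold and re-evaluated".
- Section 9.5 requires reporting within 24 hours of some bleeds below grade 3, such as those needing two or more units of red cells.
- Section 9.9 provides real-time DSMC review of serious events, weekly investigator calls, escalation of safety disagreements, and a DSMC safety review after the first 12 patients.

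Much of this stands: the harm is limited and the intent can be inferred. But an inference is not a governing clause. None of these provisions says whether the bleed counts toward 2/3, 2/6, 3/9 or 4/12, and the scheduled DSMC review comes after the looks at 3, 6 and 9 patients.

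**Conclusion.** The concern holds. The three DLT lists conflict on significant, possibly related grade 2 hemorrhage, Section 7.1.1 is the one that omits it, and nothing in the document settles which applies. Following Section 7.1.1 as written can keep 420 mg open when the other two lists would stop it; the reverse cannot happen.

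The consequence is confined to the lead-in dose decision and to how the affected patient is handled. The percentages are illustrations that rest on assumed, independent DLT rates and, in Step 3, on exactly one such bleed among 12 patients. The conflict between the lists needs no assumption.

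**What to change.** Use the Section 13 list in all three places.

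1. Add Section 13's hemorrhage bullet to Section 7.1.1: grade 3 or higher regardless of attribution, or grade 2 if at least possibly related to ibrutinib and judged significant by the treating physician with the PI.
2. In the third DLT bullet of Section 7.1.1 and of the synopsis, remove bleeding so that it reads as in Section 13 (infection or cardiac toxicity). Bleeding is then defined once in each list. In the synopsis this only removes a redundancy; the substantive correction is item 1.

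The cost is protocol wording: one bullet added and one bullet reworded in two places. The stopping limits, sample size and analyses stay as they are.

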7.1.2 Randomized Double-Blind Phase 2 Study

In the phase 2 portion of the study, patients will be randomized in a 1:1 fashion to receive ibrutinib plus standard care for COVID-19 versus placebo plus standard treatment for COVID-19. The study is double blinded and each patient will be assigned a randomization number by the James blind pharmacy. The patient, treating physicians, study personnel, and outcome assessors will all remain blinded to group assignment until after the database is locked and blinded analysis is completed. Only the unblinded statistician and the pharmacy staff have access to the unblinded randomization list.

Patients may receive any additional therapies that are not prohibited in the section on concomitant medications. In this trial, cycles will be 7 days in length. Ibrutinib therapy will continue for 2 cycles (14 days). Dose of study drug should be held or modified for adverse events as outlined in **Section 7**.

Patients who develop respiratory failure but are determined by the principal investigator to have clinical benefit from treatment may continue on for the full course of treatment.

